To date, there remains a paucity of robust evidence regarding the risk factors, incidence, and outcomes in major abdominal surgery. Firstly, there is a lack of contemporary data on cardiovascular outcomes with the recent consensus definitions for the Standardized Endpoints in Perioperative Medicine (StEP) initiative.¹³ New data assessing rates of these new composite cardiovascular endpoints would provide benchmarking data for future randomised controlled trials. Secondly, there are limited European guidelines regarding the prevention (i.e. perioperative beta-blocker therapy) and/or management of cardiovascular complications. Royal College of Anaesthetists Guidelines for the Provision of Anaesthesia Services (GPAS) provide a number of risk reduction strategies and standards within the pre-, intra- and post-operative periods. In addition, relevant Enhanced Recovery After Surgery (ERAS) protocols exist to minimise postoperative cardiovascular complication.²¹ Further, risk modification (i.e. anaemia, frailty) on postoperative cardiovascular complications remain an area of uncertainty.²²

CASCADE (CArdiovaSCular outcomes after major abDominal surgEry) aims to increase our understanding of variability and adherence to risk reduction measures for postoperative cardiovascular complications following major abdominal surgery through an international, multicentre study across Europe.

Audit Standards

* *Relevant audit standards from selected American College of Cardiology (ACC) / American Heart Association (AHA), Enhanced Recovery after Surgery, National Institute of Clinical Excellence guidelines*

Pre-operative Standards	
1. Weight and body mass index should be recorded.	
Royal College of Anaesthetists: Guidelines for the Provision of Anaesthesia Services 2021²³
 
 • Pre-operative Assessment and Preparation Recommendation 12.44: Medical records should include the patient's weight and body mass index (BMI)

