 - Staged with a planned return for reoperation (such as but not limited to damage control laparotomy or burns surgery) OR
 - Change in operative plan such that during the first procedure it is determined that a reoperation is necessary, even if the patient was enrolled preoperatively
- **Return to theatre:** Each individual patient should only be included in the study *once*. Patients returning to theatre due to complications following earlier surgery can be included, as long as their indexed procedure has not already been included in the CASCADE audit.

You should collect data on consecutive patients operated at your centre during the data collection period. This means that all eligible patients should be included.

Strategies to identify consecutive eligible patients could include:

- *Daily review of elective theatre lists.*
- *Daily review of handover sheets/ emergency admission and ward lists.*
- *Daily review of theatre logbooks (both elective and emergency).*

6. Covariates:

Data will be collected on audit standards and confounding factors for risk-adjusted analyses. These include age, sex, ethnicity, body mass index, American Society of Anaesthesiologists (ASA) grade, relevant comorbidities, smoking status, anticoagulant or antiplatelet use, preoperative blood test values, and preoperative anaemia management. Variables including operative urgency, operative procedure, operative contamination, use of tranexamic acid, intraoperative blood transfusions used, haemoglobin level at transfusion, duration of procedure and post-operative iron therapy will also be collected. Without appropriately adjusting for risk factors, it is likely that any findings would be biased and unable to be appropriately analysed on a national scale. A full list of required data fields is available in **Appendix B**, and on the REDCap database.

7. Outcome Measures and Follow-up:

Primary outcome measure:

- Rates of compliance to pre-, intra-, and postoperative audit standards in reducing risk of postoperative cardiovascular complication.

Secondary outcome measures:

- Incidence of postoperative cardiovascular complications within 30-days of surgery according to the Standardized Endpoints for Perioperative Medicine (StEP) cardiovascular.¹³ (see **Appendix D: Definitions of Key Outcomes**).
- 30-day postoperative blood transfusion rates
- 30-day complication rates defined according to the Clavien-Dindo classification (see **Appendix D: Definitions of Key Outcomes**)

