REDCap accounts will not be issued until evidence is sent to your university's regional lead that the following approvals are in place at your centre:

- *Successful registration of CASCADE with the audit department.*
- *Caldicott Guardian permission for data to be submitted to REDCap.*

11. Quality assurance:

Design: This protocol was written with guidance from an expert cross-speciality advisory group.

Training: CASCADE Regional Leads are encouraged to hold local meetings with collaborating teams at their medical school to brief them on the protocol, and to feedback any local issues or questions raised. To ensure collaborators understand the study topic, inclusion criteria, primary outcomes, application of the Clavien-Dindo classification and the principles of data governance, they will all be asked to complete online **e-learning** on these (pass mark is 100%) prior to starting data collection (online at: <https://incept.ac.uk/course/view.php?id=7>).

Project team structure: Medical students will take the lead in disseminating and delivering this study alongside junior doctors. These 'mini-teams' should be supervised by up to two consultants (two surgeons or anaesthetists) at each site in the UK & Ireland, and by a consultant per surgical specialty in the rest of Europe (**Figure 1**). Each team should include at least one qualified doctor to provide additional local support for participating medical students.

[figure not shown]

Figure 1: STARSurg “Mini-team” structure, roles, and responsibilities.

Data completeness: Following data collection, only data sets with >95% data completeness will be accepted for pooled national analysis. To emphasise the importance of data completeness to collaborators, data collection periods with >5% missing data points will be excluded from the study and collaborators from those periods withdrawn from the published list of citable collaborators.

Validation: This methodology for student-driven snapshot audit has been widely validated across multiple datasets, both nationally in the UK and Ireland and internationally, demonstrating high levels of case ascertainment (typically greater than 90 to 95%) and data accuracy (greater than 96 to 98%).^{29,30}

12. Authorship:

In accordance with National Research Collaborative (NRC) authorship guidelines³, all research outputs from CASCADE will be listed under a single corporate authorship (“STARSurg Collaborative & EuroSurg Collaborative”).

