 - Sponsorship of local audit registration, and responsible to ensure local collaborators act in accordance with local governance guidelines.
 - Inclusion of at least one data collection period at their centre which meets the criteria for inclusion within the CASCADE dataset.
 - Facilitation of local audit results presentation and support of appropriate post-audit interventions.
 - Completion of workplace-based assessments for students or trainees

(ePortfolio/ISCP), if requested.

Criteria for centre inclusion within CASCADe:

- Obtain of all appropriate local approvals for conduct of the CASCADe audit.
- Successful completion of at least one data collection period at the centre (with a minimum of one eligible patient per period included). Individual data collection periods will only be included when:
 - i. >95% data completeness has been achieved.
 - ii. All data for the period has been uploaded within the specified deadlines.

Please note if these criteria are not met, then the contributing mini-team and/or the centre may be removed from the dataset and authorship list (please get in contact as soon as potential issues arise so we can support as many centres to be included as possible). See **Appendix F** for advice to help ensure for successful inclusion of your centre in the CASCADe audit.

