Appendix B: Data Dictionary

Pre-operative Data Fields	Required data (definition / comment)	Suggested source(s)
1. Patient age	Years (whole years at the time of operation)	– Clinical letters / notes
2. Patient sex	Male / Female	– Clinical letters / notes
3. Patient body mass index (BMI)	kg/m² (record to two decimal places)	– Drug charts – Clinical letters / notes
4. Patient ASA grade	Grade I-V (Full ASA classification available at: https://www.asahq.org/resources/clinical-information/asa-physical-status-classification-system)	– Anaesthetic notes
5. Smoking status	Current (≤6 weeks, >6 weeks), Previous, Never	– Admissions clerking – Clinical notes
6. Clinical Frailty scale	1-3 / 4-6 / 7-9 (Full Clinical frailty scale available at: https://www.dal.ca/sites/gmr/our-tools/clinical-frailty-scale.html)	– Admissions clerking – Clinical notes
7. History of cardiovascular disease	Yes (myocardial infarction, angina, congestive cardiac failure, TIA/stroke, hypertension, peripheral vascular disease, atrial fibrillation, VTE, pulmonary embolism) / No If congestive cardiac failure, what is the NYHA: I / II / III / IV	– Admission clerking – Anaesthetic notes – Outpatient letters
8. History of respiratory disease	None / Dyspnoea on exertion or CXR (mild COPD) / Dyspnoea limiting exertion to <1 flight or CXR moderate COPD / Dyspnoea at rest/rate >30 at rest or CXR (fibrosis or consolidation)	
9. History of COPD	Yes / No	
10. History of chronic kidney disease	Yes (I / II / IIIA / IIIB / IV / V) / No	
11. History of liver cirrhosis	Yes / No	
12. History of diabetes mellitus	Yes - Type I / Yes - Type II (diet controlled, tablet controlled, insulin controlled) / No	
13. Active cancer and/or cancer treatment	Yes / No	
14. Inflammatory bowel disease	Yes / No	
15. Previous history of VTE	Yes / No	
16. Management of iron-deficiency anaemia	None / Preoperative iron supplementation / Tranexamic acid / RBC transfusion (If yes: 1, 2, 3, 4, ≥5 units)	
17. Preoperative treatment	Yes (Aspirin, ACEi/ARB, β-blocker, α ₂ agonist, rate controlling CCB, DHP CCB) / No If yes, was medication stopped preoperatively? (No / Yes, stopped preop only / Yes, stopped preop & postop)	– Clinical letters / notes PACS software
18. Preoperative therapeutic anticoagulation	Yes (Low Molecular Weight Heparin (LMWH), Warfarin, Direct acting oral anticoagulants (DOACs)) / No	– Clinical letters / notes PACS software

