19. Pre-admission blood tests	Haemoglobin (grams / litre) / Albumin (grams / litre) / Creatinine (ml / min) *Include blood tests taken within the 90 days prior to operation. If multiple blood tests have been taken during this period, record the lowest value. If no pre-admission blood tests are available, please record this as 0.	– Pathology systems
20. Admission blood tests	Haemoglobin (grams / litre) / White cell count (x10 ⁹ / l) / Albumin (grams / litre) / Sodium (mmol/l) / Potassium (mmol/l) / Urea (mmol/l) / Creatinine (ml / min)	– Pathology systems

	*Include the first blood test results from this admission. Only include blood tests taken before surgery	
21. Admission observations	Pulse rate (bpm) / Systolic blood pressure (mmHg) / Glasgow coma scale	–
22. Pre-operative assessment	If elective: Yes (pre-admission anaesthetic assessment clinic) / No. If yes: Did this include pre-operative cardiopulmonary exercise testing (Yes - VO ₂ peak, AT / No). If emergency: Yes (inpatient perioperative or elderly medicine, including physician or nurse specialist) / No	– Clinical letters / notes
23. Preoperative investigations	None / ECG (normal / abnormal) / Echocardiography (LVEF, %) / Coronary angiography	–
Abbreviations: ASA = American Society of Anaesthesiologists; Hb = Haemoglobin; LVEF = Left Ventricular Ejection Fraction PACS = Picture Archiving and Communication.		

Intra-operative Data Fields	Required data (definition / comment)	Suggested source(s)
1. Prior Operations	1 / 2 / >2	
2. Operative urgency (NCEPOD Classification of Intervention)	Immediate (Immediate life, limb or organ-saving intervention - resuscitation simultaneous with intervention. Normally within minutes of decision to operate). Urgent (Intervention for acute onset or clinical deterioration of potentially life-threatening conditions, for those conditions that may threaten the survival of limb or organ, for fixation of many fractures and for relief of pain or other distressing symptoms. Normally within hours of decision to operate) Expedited (requiring early treatment where the condition is not an immediate threat to life, limb or organ survival. Normally within days of decision to operate). Elective (Intervention planned in advance of routine admission to hospital).	– Operative note – Admissions clerking
3. Primary indication	Malignant / Benign If malignant: Primary only / nodal metastases / Distant metastases	– Operative note. – Clinical notes. – Theatre records.

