10. Regularly follow-up for information on complications over the 30-day post-operative period. This study is prospective, so you should not wait until the end of the post-operative period to

follow-up patients (this would be retrospective). Discuss the best way to follow up patients with the consultant supervising your audit, as this will vary from centre to centre.

Be proactive in identifying post-operative adverse events, as this will prevent under-estimation of true complication rates. Remember that in this audit no changes to normal patient follow-up should be made.

Strategies for identifying complications in the follow-up period include:

- *Regularly reviewing patient notes to identify in-hospital complications.*
- *Reviewing clinic notes and clinic letters, if seen in clinic by 30 days.*
- *Checking electronic systems and handover lists for re-admissions.*
- *Checking for A&E re-attendances.*

If case notes are reviewed shortly prior to discharge they do not need to be requested/retrieved again for follow-up at 30-days, but do check electronic records for discharge letters, clinic letters, re-admissions.

11. Ensure all data has been uploaded to the REDCap system by the data collection deadline, and you have completed all fields, avoiding missing data points. If more than 5% of patients at your centre have missing data, your centre cannot be included in the CASCADE dataset and your name will be withdrawn from the author list.
12. It is a condition of participation in CASCADE that following completion of the audit at your centre you must ensure that your local results are presented to your hospital's surgical department and/or reported back to the audit department. You may also like to return to present again at a later date, when the final national results of CASCADE become available.

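### The protocol gives two incompatible missing-data exclusion rules, and an unrecorded BMI, which fails an audit standard, can appear only as missing data

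*Protocol*

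**What the plan says.** Completeness is governed in three places in the protocol.

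- **Section 11, Data completeness:** "data collection periods with >5% missing data points will be excluded from the study". The count is of data points and the unit removed is the period.
- **Section 12, Criteria for centre inclusion:** a period counts only when ">95% data completeness has been achieved". If the criteria are not met, "the contributing mini-team and/or the centre may be removed from the dataset and authorship list".
- **Appendix E, step 11:** "If more than 5% of patients at your centre have missing data, your centre cannot be included in the CASCADE dataset". The count is of patients, the unit removed is the centre, and there is no discretion.

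The primary outcome (section 7) is "Rates of compliance to pre-, intra-, and postoperative audit standards in reducing risk of postoperative cardiovascular complication". Pre-operative standard 1 reads "Weight and body mass index should be recorded". In Appendix B the BMI field is numeric only, "kg/m² (record to two decimal places", and the Appendix A form is the same. Neither appendix has a field for weight. Other fields do have a code for absent information. For pre-admission bloods the instruction is "If no pre-admission blood tests are available, please record this as 0", and haemoglobin at transfusion and on readmission each have a *not available* option.

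**The concern.** There are two linked problems.

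First, the rules differ in what is counted (data points or patients), in what is removed (period or centre) and in force (section 12 leaves room for judgement, Appendix E does not). Which centres form the dataset then depends on which sentence the study team follows.

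Second, where the standard is that something be recorded, failing it and having a missing value are the same event unless the form separates them. This form does not. An exclusion rule based on missing values therefore acts on a component of the primary outcome. In the database, a BMI that the clinical team never recorded cannot be told apart from one that the collaborator did not enter. The second is a data-quality problem; the first is an audit result.

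**Working it through.** **Inputs from the protocol.** About 300 centres and ten patients per centre per week (section 9), with a 14-day collection period (section 1). This reproduces the protocol's own figure: 300 × 10 × 2 = 6000 patients, or 20 per centre-period.

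**Assumed inputs.** The protocol does not state the number of data points per patient. Appendix B has 23 + 12 + 15 = 50 numbered items, some with several values, so I use 40, 50 and 60. It gives no true BMI recording rate; I use 80% and 90%.

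**1. Do the rules agree?** Let 1% of data points be missing, independently.

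*Section 11.* With 50 fields there are 20 × 50 = 1000 data points, and up to 50 may be missing. The expected number missing is 10, with SD √(1000 × 0.01 × 0.99) ≈ 3.1. The limit is more than 12 SDs away, so essentially every period passes.

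*Appendix E.* The chance that a patient has at least one missing field is q = 1 − 0.99^F. With 20 patients, one incomplete patient is exactly 5% and is allowed; two are not. So P(pass) = (1 − q)^20 + 20q(1 − q)^19.

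| Fields F | q | P(centre passes Appendix E) |
|---|---|---|
| 40 | 33.1% | 0.35% |
| 50 | 39.5% | 0.06% |
| 60 | 45.3% | 0.01% |

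With 0.1% of data points missing, the same formula gives 82%, 74% and 67%.

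**2. What does each rule do to standard 1?**

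*Appendix E.* If at most 5% of a retained centre's patients have any missing field, at most 5% can lack BMI. Recording among retained centres is then at least 19/20 = 95%. This needs no assumption about true practice.

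*Section 11.* BMI absent in all 20 patients is 20 of 1000 data points, or 2.0% (20/800 = 2.5% with 40 fields, 20/1200 = 1.7% with 60). If little else is missing, a period with 0% BMI recording is kept, so there is no floor. Those 20 points still use up part of the allowance of 50.

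**3. Illustration under Appendix E.** Take n = 20, the same true rate p in every centre, and BMI as the only missing field. The share kept is p^20 + 20(1 − p)p^19. Reported recording among kept centres is 1 − (1/20) × P(exactly one missing) / P(kept).

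| True rate | P(none missing) | P(one missing) | Kept | Reported |
|---|---|---|---|---|
| 80% | 1.15% | 5.76% | 6.9% (about 21 of 300) | 95.8% |
| 90% | 12.16% | 27.02% | 39.2% (about 118 of 300) | 96.6% |

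The share kept is sensitive to spread between centres. In a simulation with beta-distributed centre rates, a mean of 80% with SD 15 points gives 28% kept and 97% reported. A mean of 90% with SD 8 points gives 51% kept and 98% reported. The reported rate changes little.

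**The case against.** The best defence is that Appendix E is guidance to collaborators, while sections 11 and 12 are the formal criteria. Both of those work per period, and section 11 names data points. Step 11 itself tells collaborators to avoid missing data points just before it states the patient-based rule, so that sentence may be a loose paraphrase. If so, correcting it removes the 95% floor. This is a fair reading, and it is why the floor is stated here as conditional. It does not remove the contradiction: the step states an exclusion rule without qualification and attaches loss of authorship to it.

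A reader might infer that compliance with standard 1 is at least 95% by construction, or that the primary outcome as a whole is fixed in advance. The documents do not support either. The floor follows from Appendix E alone, and it concerns one of nine listed standards. The WHO checklist and exercise testing, for example, are Yes/No items, so a *No* is complete data. Nor do the documents show that centres with poor BMI recording comply less with other standards. And the two rules do not always disagree: near-complete data pass both and very incomplete data fail both.

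The magnitudes rest on assumed inputs. Missingness clustered within patients would leave fewer patients incomplete than independence implies. A centre contributing several periods would have more than 20 patients, which changes the share kept but not the floor.

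Lastly, the REDCap form is not shown and may contain a *not recorded* answer. The printed dictionary, which section 6 cites for the full list of required fields, does not.

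**Conclusion.** The point holds in two parts.

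The contradiction between sections 11 and 12 and Appendix E step 11 is plain on the page and needs no assumption. Its practical size depends on the amount and pattern of missing data. At 1% independent missingness it is the difference between keeping nearly all periods and keeping well under 1% of centres, for any field count from 40 to 60.

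The lack of a *not recorded* answer for BMI, and of any weight field, is also plain in Appendices A and B. Under either rule, failing standard 1 counts towards exclusion. Only under Appendix E does this guarantee at least 95% BMI recording in every retained centre. The weight half of the standard cannot be measured from the listed fields at all.

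The kept and reported percentages illustrate the mechanism under assumed recording rates; they do not predict what the study will find. The matter belongs in the protocol, because it decides which data enter the dataset, and a response option that was not collected cannot be reconstructed at analysis.

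**What to change.** 1. Use one completeness rule throughout: the percentage of missing data points per collection period, as in section 11. Reword Appendix E step 11 to match, and say in section 12 whether failing it means exclusion or possible exclusion.
2. Add a weight field, and a *not recorded in notes* answer for both weight and BMI. Count that answer as complete for data quality and as non-compliant for standard 1.
3. Optionally, report compliance with each standard a second time with the excluded periods restored, so that the effect of exclusion can be seen.

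The cost is a few words in Appendix E and section 12, a small change to the form and dictionary, and, if wanted, one sensitivity table. Reported BMI compliance may be less favourable as a result.
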